9.4.4. Retreatment and Dose Delay

A new cycle of treatment may begin when the ANC is $\geq 1500/\text{mm}^3$, the platelet count is $\geq 100,000/\text{mm}^3$, and the non-hematologic toxicities are \leq grade 1, except for alopecia (for which a grade > 1 is allowed) and for ocular toxicity (for which a worsening retinopathy of 1 or more grades compared to baseline implies study treatment discontinuation) or are recovered to baseline values, if grade 2 is allowed at study entry. If these conditions have not been met, treatment should be delayed for 1 or 2 weeks to allow for recovery. If after a maximum of a 2-week delay all toxicities (except for alopecia and for toxicities for which grade 2 is allowed at study entry) are \leq grade 1, then proceed with treatment as outlined in the Dose Modification Table 4. An increased delay > 2 weeks is to be discussed between the Investigators and the Sponsor on a case by case basis.

9.4.5. Overdose Instructions

There are no known antidotes for milciclib maleate PHA-848125AC. In the case of an overdose of PHA-848125AC, neurological toxicity (tremors and ataxia) and gastrointestinal toxicity are among the expected effects. The Sponsor study management should be contacted to discuss the details of any overdose.

9.4.6. Unblinding

Not applicable in this study.

9.4.7. Assessment and Management of Potential CNS Toxicity

Signs of CNS toxicity, including tremors, hyperactivity and ultimately convulsions have been observed during the toxicology evaluations of PHA-848125AC administered at high single or high repeated doses attaining daily systemic exposures $\geq 30\mu$ M.h. In all species, this pattern of toxicity was reversible and not accompanied by morphological/pathological findings.

In humans, reversible tremors and ataxia have been reported in the CDKO-125a-001 study (see Section 3.2.7). Resolution of both events in approximately 7-8 days was reported, upon study treatment discontinuation.

Tremors which can be induced by other drugs include enhanced physiologic tremor, rest tremor, and action tremor. Signs and symptoms of drug-induced tremors depend on the drug used and on a patient's predisposition to its side effects. Cessation of the causative agent may improve drug-induced tremor symptoms. Table 5 lists drugs that may induce tremor, along with the types of tremors and neurologic signs they produce.

Tiziana Life Sciences, PLC - Confidential Page 52 of 101

Drug/Drug Class	Tremor Type	Neurologic Signs
Neuroleptics	Rest, postural	Extrapyramidal
Metoclopramide	Rest, postural	Extrapyramidal
Lithium	Rest, postural, action	Extrapyramidal
Theophylline	Postural	None
Bronchodilators	Postural, action	None
Valproate	Postural	Rarely parkinsonism
Amiodarone	Postural	Rarely parkinsonism

Table 5. Drug-induced Tremors and Corresponding Neurologic Signs

During visits, patients treated with PHA-848125AC will undergo regular clinical examination, which includes the assessment of clinical tremors and associated signs and symptoms. Patients should be examined during rest, when assuming various positions and when moving. Tremors will be graded according to NCI CTCAE version 3.0 grading system as follows:

Tremor Grades, NCI CTCAE Version 3.0
0. Absent
1. Mild and brief or intermittent but not interfering with function
2. Moderate tremor interfering with function, but not interfering with ADL
3. Severe tremor interfering with ADL
4. Disabling

PHA-848125AC dose modifications for neurologic adverse events attributable to the study drug are detailed in Table 4.

Pharmacological management of neurological adverse events, such as tremors and/or convulsions, should refer to institutional and/or published interventional protocols [35,36].

9.4.8. Assessment of Potential Ocular Toxicity

Ocular toxicity has been reported in rats treated for prolonged period of time (daily treatments for 3 consecutive weeks + 1 week of rest x 3 cycles or daily treatments for 4 consecutive weeks) at doses associated with daily AUCs close to 25 μ M·h, as well as in rats given daily treatments for 2 consecutive weeks +1 week of rest for 5 cycles at doses associated to AUC of about 32 μ M·h.

No ocular toxicity was observed in rats with a 7-day repeat treatment schedule up to doses associated to a daily AUC of about 50μ M·h or up to doses associated to a daily AUC of about 10 μ M·h in the 4-week schedule and up to doses associated to daily AUC of about 12 μ M·h. in the 3-week schedule.

Tiziana Life Sciences, PLC - Confidential Page 53 of 101

Milciclib maleate (PHA-848125AC)	CDKO-125a-006-P4
Protocol for Study CDKO-125a-006	09 March 2017

Despite clinical manifestations of ocular toxicity were not observed in the clinical studies so far, a potential ocular toxicity cannot be excluded. During visits, patients treated with PHA-848125AC will undergo regular clinical examinations, i.e. ophthalmologic examination (visual acuity test and funduscopic examination), at the end of even cycles (see Schedule of Events in Section 7 and also Section 11.4.3).

Retinopathy will be graded according to NCI CTCAE version 3.0 grading system as follows:

Reti	nopathy Grades, NCI CTCAE Version 3.0
0.	Absent
1.	Asymptomatic
2.	Symptomatic with moderate decrease in visual acuity (20/40 or better)
3.	Symptomatic with marked decrease in visual acuity (worse than 20/40)
4.	Blindness (20/200 or worse)

Grade 1 retinopathy is allowed at study entry since it is an asymptomatic event occurring in relation to common medical conditions such as hypertension [37,38]. It is recognized that several patients in their 50s and 60s with underlying hypertension may present asymptomatic retinopathy. Such a status is to be regarded as a condition which does not prevent patients' enrollment in the study, being not clinically significant.

Ophtalmologic evaluations will be possibly done by the same ophthalmologist for a given patient.

The increase of 1 or more grades retinopathy by ophthalmologic examination will require immediate study drug discontinuation.

Management of ocular adverse events should refer to institutional interventional protocols.

9.4.9. Assessment of Potential, Thrombotic Microangiopathy/Hemolytic Uremic Syndrome

Two patients, both treated in the CDKO-125a-004 combination study with gemcitabine ('A Phase I Dose-Escalation Study of Oral PHA-848125AC Administered in Combination with Gemcitabine in Adult Patients with Advanced/Metastatic Solid Tumors'), developed Thrombotic Microangiopathy/Hemolytic Uremic Syndrome (TMA/HUS). The two cases were considered to be probably related to gemcitabine and unlikely related to PHA-848125AC by the participating Investigator, and occurred in patients with very prolonged and high exposure to both drugs (after 14 and 21 months on treatment, respectively); both patients recovered in the opinion of the Investigator, and only one of them required plasmapheresis. No other cases of TMA/HUS were reported in any of the other studies completed or ongoing with PHA-848125AC (all single agent studies). Anyway, taking into consideration the small number of patients treated so far at this stage of development of PHA-848125AC (about 200 patients), a contribution of the study drug on

Tiziana Life Sciences, PLC - Confidential Page 54 of 101 the two observed TMA/HUS events cannot be completely ruled out. As a consequence, special attention should be paid to the following events:

- Progressive increase of anemia up to CTC Grade \geq 3 no otherwise explained
- Progressive platelets decrease up to CTC Grade ≥ 2
- Increase of creatinine (shift to CTC Grade 2) or calculated creatinine clearance diminished by ≥ 25% vs baseline
- Presence of hematuria or proteinuria
- Appearance of high blood pressure in a patient with unknown history or with high blood pressure previously well controlled with medications
- Appearance of oedema concomitant to proteinuria

Whenever ≥ 2 of the above listed alterations appear concomitantly for the first time, or at any time if the Investigator judges it appropriate, study drug administration is to be temporarily held, until further evaluations are done. The latter ones consisting of the search of schistocytes in the peripheral blood smear, the count of reticulocytes in the peripheral blood, coagulation test, total LDH and 24-hour proteinuria [39]. Routine Hematology, Blood Chemistry and Urinalysis tests foreseen by study protocol, should also be repeated at the time when this evaluation is performed.

If based on the above examinations MTA/HUS can be ruled out, study drug administration can be resumed, adopting the dose modifications outlined in Table 4 for drug-related toxicities, as applicable.

In case of suspicion or evidence of MTA/HUS, study drug has to be discontinued.

9.4.10. Concomitant Medications and Other Therapy

All concomitant medications must be entered into the CRF.

After the data cut-off of 31 May 2017 and protocol Amendment 4 is approved at the investigational site, data will be no longer collected into the CRF, and information on concomitant medications should continue to be recorded into the patient's medical notes only.

Directives for supportive care are outlined below.

9.4.10.1. Antiemetics

Prophylactic therapy with antiemetics is allowed starting from the first onset of emesis. Pharmacological management of nausea and/or vomiting may refer to institutional and/or published guidelines for treatment [40,41].

> Tiziana Life Sciences, PLC - Confidential Page 55 of 101

9.4.10.2. Antidiarrheals

Treatment with loperamide might be started at the occurrence of grade 1 diarrhea (increase of < 4 stools per day over baseline; mild increase in ostomy output compared to baseline). Loperamide should be taken in the following manner: 4 mg at the first onset of diarrhea, then 2 mg every 2 hours. This therapy should continue for 12 hours after the last liquid stool. Patients may take loperamide 4 mg every 4 hours during the night. In no instance should loperamide be administered for more than 48 consecutive hours because of the risk of paralytic ileus.

Other antidiarrhetic agents and/or antibiotics used by the Institutions are allowed. Patients should be instructed to refer to the center in case of diarrhea lasting > 24 hours despite optimal supportive care or diarrhea with fever.

9.4.10.3. Antiacids

Patients with chronic/ intensive use of H2-receptor antagonists, proton pump inhibitors, antacids, should take these drugs at a time point far from PHA-848125AC intake (at least 3-4 hours) during the day, or the night before treatment, to avoid any potential effect on PHA-848125AC absorption.

9.4.10.4. Hematopoietic Growth Factors

Hematopoietic growth factors may be used as medically indicated in patients with relevant neutropenic complications, such as tissue infection, sepsis, etc., at the Investigator's discretion. Red blood cell and/or platelets transfusion should be considered at the Investigator's discretion in patients with significant anemia and/or thrombocytopenia.

9.4.10.5. Anticoagulants

Concomitant anticoagulant treatment is not recommended.

9.4.10.6. Inhibitors or Inducers of CYP3A4

Significant drug-drug interactions with inhibitors or inducers of CYP3A4 are not expected (see Section 3.2.4). Therefore, there are no specific contraindications to the use of inhibitors or inducers of CYP3A4.

9.4.10.7. Steroids

Concurrent use of steroids for treatment of a pre-existing autoimmune disorder or as antiemetic therapy is allowed.

Tiziana Life Sciences, PLC - Confidential Page 56 of 101

9.4.10.8. Other Permitted Concomitant Medications

Therapies considered necessary for the patient's well being may be given at the discretion of the Investigator, i.e. chronic treatments for concomitant medical conditions, as well as agents required for life-threatening medical problems, analgesics etc. Patients should be advised to contact the treating physician before starting any new drug.

9.4.10.9. Concomitant Radiotherapy

Palliative radiotherapy to specific sites is permitted if considered medically necessary by the treating physician. However, the irradiated area should be as small as possible, and involve $\leq 20\%$ of the bone marrow reserve [Appendix 2]. During the period of irradiation and for 2 weeks after, chemotherapy should be withheld. If irradiation-related toxicities (other than xerostomia) have not normalized to pre-irradiation levels after these 2 weeks of rest, the patient should be removed from the study. Radiotherapy should be avoided for at least 5 days after the last dose of PHA-848125AC.

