4.2.2. Secondary Endpoints

- Confirmed Objective Response Rate (CR + PR) according to RECIST guideline (version 1.1).
- Disease Control Rate (Confirmed Objective Response Rate $+ \ge 6$ weeks SD rate).
- Progression-free survival, calculated as the time from the date of treatment start to the date of first documentation of objective progression or of death due to any cause, whichever comes first.
- Duration of Response, measured from the time measurement criteria are first met for CR/PR (whichever is first recorded) until the first date that recurrent or progressive disease is objectively documented (taking as reference for progressive disease the smallest measurements recorded on study).
- Overall Survival (OS), i.e. the time from the date of treatment start to the date of death from any cause.
- Overall safety profile, evaluated on the basis of laboratory and clinical safety parameters (i.e. hematology and blood chemistry, urinalysis, vital signs, ophthalmologic examinations and adverse events emerging during the trial). The National Cancer Institute Common Terminology Criteria for Adverse Events (NCI CTCAE) Version 3.0 will be used for the severity grading of adverse events and of hematological and blood chemistry abnormalities.

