9.4.10.10. Other Anticancer or Experimental Therapy

No other approved or investigational anticancer treatment will be permitted during the study period including chemotherapy, biological response modifiers, hormones or immunotherapy. No other investigational drug may be used during therapy on this protocol. Simultaneous participation in other clinical treatment study protocols is not allowed.

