• Lesions that meet the criteria for radiographically defined simple cysts should not be considered as malignant lesions (neither measurable nor non-measurable) since they are, by definition, simple cysts.

• "Cystic lesions" thought to represent cystic metastases can be considered as measurable lesions, if they meet the definition of measurability described above. However, if non-cystic lesions are present in the same patient, these are preferred for selection as target lesions. *Lesions with prior local treatment:*

• Tumor lesions situated in a previously irradiated area, or in an area subjected to other locoregional therapy, are usually not considered measurable unless there has been demonstrated progression in the lesion.

When effusions are known to be a potential adverse effect of treatment, the

cytological/histological confirmation of the neoplastic origin of any effusion that appears or worsens during treatment when the measurable tumor has met criteria for response or SD is mandatory to differentiate between response or SD and PD.

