Target lesions that become "too small to measure": while on study, all lesions (nodal and non-nodal) recorded at baseline should have their actual measurements recorded at each subsequent evaluation, even when very small (e.g. 2 mm). However, sometimes lesions or lymph nodes which are recorded as target lesions at baseline become so faint on CT scan that the radiologist may not feel comfortable assigning an exact measure and may report them as being 'too small to measure'. When this occurs it is important that a value be recorded on the case report form. If it is the opinion of the radiologist that the lesion has likely disappeared, the measurement should be recorded as 0 mm. If the lesion is believed to be present and is faintly seen but too small to measure, a default value of 5 mm should be assigned. (Note: It is less likely that this rule will be used for lymph nodes since they usually have a definable size when normal and are frequently surrounded by fat such as in the retroperitoneum; however, if a lymph node is believed to be present and is faintly seen but too small to measure, a default value of 5 mm should be assigned in this circumstance as well). This default value is derived from the 5 mm CT slice thickness (but should not be changed with varying CT slice thickness). The measurement of these lesions is potentially non-reproducible, therefore providing this default value will prevent false responses or progressions based upon measurement error. To reiterate, however, if the radiologist is able to provide an actual measure, that should be recorded, even if it is below 5 mm. Lesions that split or coalesce on treatment: when non-nodal lesions "fragment", the longest diameters of the fragmented portions should be added together to calculate the target lesion sum. Similarly, as lesions coalesce, a plane between them may be maintained that would aid in obtaining maximal diameter measurements of each individual lesion. If the lesions have truly coalesced such that they are no longer separable, the vector of the longest diameter in this instance should be the maximal longest diameter for the "coalesced lesion".

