12. STATISTICAL METHODS

12.1. Sample Size Calculation

In consideration of the exploratory nature of the study, the Simon's optimal 2-stage design [42] is adopted for this single-arm, open-label, multicentre phase II clinical trial.

The total number of evaluable patients for the primary efficacy analysis ranges from 17 (if the trial stops at the end of the 1st step) to 54 (if the trial proceeds up to the completion of the 2^{nd} step). Accounting for a 10%-15% proportion of non evaluable patients, up to 20

Tiziana Life Sciences, PLC - Confidential Page 74 of 101

Milciclib maleate (PHA-848125AC)	CDKO-125a-006-P4
Protocol for Study CDKO-125a-006	09 March 2017

patients could be required in the 1st stage of the study and up to 60 patients could be required for completing the trial (1st and 2nd stage).

The primary endpoint of the study is the progression-free survival status at 3 months and the primary efficacy analysis will be performed on the proportion of successes (i.e. patients alive and in a progression-free status at 3 months since treatment start) out of the total number of evaluable patients (PFS-3 rate).

Considering a 33% PFS-3 rate as clinically interesting, against a clinically uninteresting hypothesis of a PFS-3 rate no higher than 17%, the system of hypotheses to be tested is:

*H*₀: $p \le p_0$, $p_0 = 0.17$ vs. *H*₁: $p \ge p_1$, $p_1 = 0.33$

The analysis will be performed at the overall level $\alpha = 0.05$ (1-sided). The design below outlined will provide 80% power (1- β) not to reject the treatment as insufficiently effective, if the true PFS-3 rate is 33% or higher.

In the first stage, 17 evaluable patients are to be assessed. If \leq 3 successes are observed, the study treatment will be considered as providing insufficient evidence of efficacy and the trial will be terminated.

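### The protocol permits palliative radiotherapy to target lesions but has no rule for scoring a lesion irradiated on study, so local control by radiation can count as a PFS-3 success or a confirmed response

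*Protocol*

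**What the plan says.** Section 9.4.10.9 allows radiotherapy during treatment: "Palliative radiotherapy to specific sites is permitted if considered medically necessary by the treating physician". Its conditions are a field as small as possible, a cap on the marrow irradiated, withholding of treatment during irradiation and for 2 weeks after, removal from the study if irradiation toxicity persists, and a gap of at least 5 days after the last dose. None concerns target lesions or the 3-month assessment.

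Section 9.4.10.10 bars other tumour-directed drugs: "No other approved or investigational anticancer treatment will be permitted during the study period including chemotherapy, biological response modifiers, hormones or immunotherapy". Radiotherapy is not in that list.

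A success in Section 12.1 is defined by "patients alive and in a progression-free status at 3 months since treatment start". Sections 4.2.1 and 12.3.4 define it in the same way, adding that the status must be known. In Section 4.2.2 PFS runs to the "date of first documentation of objective progression or of death due to any cause, whichever comes first".

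For on-study measurement, Section 11.2.1.3 says that "all lesions (nodal and non-nodal) recorded at baseline should have their actual measurements recorded at each subsequent evaluation". The response definitions there and Table 6 have no category for a lesion irradiated on study. The only rule on irradiation is in Section 11.2.1.1: "Tumor lesions situated in a previously irradiated area, or in an area subjected to other locoregional therapy, are usually not considered measurable", unless progression in the lesion has been shown. That section classifies lesions at baseline.

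**The concern.** The primary objective (Section 4.1.1) is the drug's antitumour activity, judged in a single arm. Radiotherapy is the one tumour-directed treatment allowed alongside the drug, and it acts on the same lesions that decide the endpoint.

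Consider a patient whose target lesion is growing but is still below the 20% increase that defines progression. The lesion is irradiated for symptoms, and at days 92 to 98 it is stable or smaller. Under the rules as written the patient is progression-free and counts towards the 4/17 and 14/54 thresholds. If the sum has fallen by 30% and this is confirmed at least 4 weeks later, the patient is also an objective response. Stable disease of at least 6 weeks that rests on the irradiated lesion enters the disease control rate.

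The need for radiotherapy is not a PFS event, nor is it a listed reason for withdrawal in Section 10. Section 11.2.1.6 treats symptomatic deterioration as a reason for stopping therapy, not as a response category. The evaluable population in Section 12.2 does not exclude irradiated patients, and the supportive analyses in Section 12.3.4 do not separate them.

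**Working it through.** **Inputs.** From Section 12.1: null rate 0.17, target rate 0.33, one-sided α 0.05, power 0.80. Stage 1 has 17 evaluable patients and stops at 3 or fewer successes. The total is 54, and at least 14 successes are needed to reject the null. The number of successes produced by radiotherapy is not in the protocol. It is assumed below to average 1, 2 or 3 per 54.

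**Formula.** With true success probability p, the chance of declaring the drug active is

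P(p) = Σ (x = 4 to 17) P[Bin(17, p) = x] × P[Bin(37, p) ≥ 14 − x].

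**The plan's own figures.**
- p = 0.17: P = 0.0496, probability of early termination 0.675, expected sample size 17 + (1 − 0.675) × 37 ≈ 29.0.
- p = 0.33: P = 0.806, probability of continuing 0.863.

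These match the stated design. A search for the Simon optimal design at these inputs returns the same rule (3/17, 13/54). The exact α of 0.0496 leaves almost no slack below 0.05.

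**Effect of radiation-made successes on an inactive drug.** Set p = 0.17 + m/54, where m is the assumed average number of would-be failures per 54 that become successes through radiotherapy.

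| m per 54 | p | Passes stage 1 | Declared active |
|---|---|---|---|
| 0 | 0.1700 | 0.325 | 0.0496 |
| 1 | 0.1885 | 0.403 | 0.098 |
| 2 | 0.2070 | 0.480 | 0.170 |
| 3 | 0.2256 | 0.555 | 0.262 |

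**Cost of scoring such patients as non-successes.** If the 33% target already includes m of them per 54, the rate falls to p = 0.33 − m/54.

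| m per 54 | p | Power |
|---|---|---|
| 0 | 0.3300 | 0.806 |
| 1 | 0.3115 | 0.736 |
| 2 | 0.2930 | 0.649 |
| 3 | 0.2744 | 0.549 |

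**Does another rule close the gap?**
- The baseline measurability rule does not. It governs which lesions qualify at entry.
- The stop on follow-up imaging at a new antitumour therapy (Section 11.2.1) is written for patients already off study treatment.
- The requirement of at least 80% of drug in the first two cycles (Section 12.2) covers 2 × 14 = 28 days. It may remove some patients irradiated early. It does not reach irradiation from about day 29 up to the scan at days 92 to 98.

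**The case against.** The strongest reply is that a false success needs several things at once. The irradiated lesion must be the one that would have driven progression, it must be below the 20% threshold when treated, and nothing else may progress while treatment is withheld. Section 11.2.1 provides a scan at days 42 to 48 and imaging at clinical deterioration, so progression may be recorded before irradiation. New lesions and unequivocal non-target progression still count. All of this stands, and it limits how often the problem can occur.

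A second reply is that handling of concomitant therapy in PFS often belongs in an SAP, and one may exist. This stands in part: a missing censoring rule would be no finding. Here, however, the protocol itself fixes both the success definition and the lesion rules applied at each scan. As written they classify an irradiated, shrunken lesion as stable or responding, so an SAP rule would have to override them.

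Three stronger readings are tempting, and the documents do not support them:
- A reader might infer that radiotherapy is unrestricted in time. Section 9.4.10.9 sets the 5-day gap and the treatment hold.
- A reader might infer that the net bias always favours the drug. The scoring rule can only add successes, but the hold may let other sites progress. The protocol also does not say whether the cited study behind the 17% null allowed palliative radiotherapy.
- A reader might infer a very large inflation by supposing that a tenth of would-be failures are converted. That means 0.10 × 0.83 × 54 ≈ 4.5 such patients, each meeting every condition above, and nothing in the protocol supports it.

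**Conclusion.** The concern holds as a gap in the scoring rules. Radiotherapy to a target lesion is permitted before the 3-month assessment, the lesion stays in the sum, and its control can be credited as PFS-3 success, response or stable disease. It is a possibility that the text allows, not a demonstrated inflation. On the assumption of one radiation-made success per 54 patients on average, the type I error roughly doubles to 0.098; with two it is 0.170. These figures rest on the assumed counts and on a true drug-only rate of 17%. Because the exact α has almost no slack, even a rare event matters to the decision, so the rule should be settled before the data are read. Whether radiotherapy should be permitted is a clinical matter and is not judged here.

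**What to change.** In Section 4.2.1, Section 12.3.4 and the synopsis, state that an evaluable patient as defined in Section 12.2 who receives radiotherapy before the 3-month assessment is not a PFS-3 success and stays in the evaluable denominator, if the radiotherapy was to a target lesion or to a lesion that is growing or newly symptomatic from tumour. Limiting the rule in this way avoids failing patients irradiated at an unrelated, stable non-target site. It also leaves the composition of the primary population as it is.

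In Section 11.2.1.3, state that a response or stable disease that depends on a target lesion irradiated on study is not credited from the date of irradiation, while progression at any site still counts.

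Record the site and date of on-study radiotherapy in the CRF. Report the PFS-3 count by scan alone as a sensitivity analysis, so that the influence of the rule can be seen.

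The cost is a few sentences and one data field. The PFS-3 rate may be slightly less favourable. If the 33% target includes one such patient per 54, power falls from 0.806 to 0.736, and further if there are more. Who may receive radiotherapy, and under what conditions, does not change.
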